1.5 Photographic Cosmetic Assessment

There are no validated photographic assessment tools in patients with breast reconstruction. The EORTC Breast Cosmetic Rating system is a digital photographic method that has been utilized in prior radiation studies and shown to be reliable and valid in detecting effects of radiation morbidity. [45-47] This method compares the radiated breast with the contralateral untreated side and evaluates: Size, shape, location of the areola/nipple, appearance of the surgical scar, skin pigmentation changes, presence of telangiectasia and a global cosmetic score based on all of the factors. Characteristics are graded on a four-point scale: 0, excellent or no difference; 1, good or small difference; 2, fair or moderate difference; and 3, poor or large difference.

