2.3 Photographic Cosmetic Assessment

- 2.3.1** To evaluate reconstructed breast photographic cosmetic scores with hypofractionated radiation compared to standard fractionation 24 months after radiation.
- 2.3.2** To evaluate reconstructed breast photographic cosmetic scores 24 months after radiation based on the method and timing of reconstruction received.

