4.6 Stratification Factors and Treatment Assignments

The factors listed below will be used as stratification factors. After a patient has been registered, the values of the stratification factors will be recorded, and the patient will be assigned to either hypofractionated or standard radiation dosing using the Pocock and Simon dynamic allocation

procedure, which balances the marginal distributions of the stratification factors between the treatment groups (Pocock-Simon).

Patients will be stratified before randomization based on planned intent for:

- autologous (+/- implant) vs.
- implant only breast reconstruction.
- Patients will be stratified before randomization based on:
 - immediate reconstruction vs.
 - planned for delayed breast reconstruction (**includes patients who have had no reconstruction or only a temporary expander placed at time of randomization.**)
- ** Patients undergoing immediate reconstruction will already have completed reconstruction at the time of randomization.
- *** Patients who have a tissue expander placed at the time of mastectomy and then have a delayed final reconstruction will be classified as delayed for purposes of stratification and randomization.

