Simulation studies of 10,000 clinical trials are conducted for the proposed group sequential design. The probabilities of early stopping (at the interim analysis) and empirical powers for various scenarios are summarized in the following table. Of particular interest, assuming that the two-year breast reconstruction complication rate is 25% for the control arm (Arm 1: conventional PMRT) and 35% for the hypofractionated PMRT (Arm 2), where the Arm 2 treatment is inferior to Arm 1, there is a 14.45% chance of stopping the trial early to conclude that hypofractionated PMRT is inferior. In another scenario where the complication rate of the conventional PMRT is 25% and that of hypofractionated is 25%, where the Arm 2 treatment is truly non-inferior to Arm 1, the likelihood of stopping early to conclude inferiority is 0.24% and the likelihood of the trial concluding that hypofractionated PMRT is non-inferior to conventional one is 90.84% (power).

Reconstruction complication rate		Interim analysis conclusion		Early stopping	Final analysis conclusion		Rejection (of H_0) rate
Conventional	Hypofractionated	Noninferior	Inferior		Noninferior	Inferior	
25%	35%	0.00%	14.45%	14.45%	2.37%	83.18%	2.37%
	30%	0.00%	2.86%	2.86%	34.51%	62.63%	34.51%
	25%	0.00%	0.24%	0.24%	90.84%	8.92%	90.84%

It should be noted that the primary analyses will be an intent-to-treat analysis where all patients randomized will be included in the analysis and will be analyzed based on the arm they were randomized to regardless of actual radiation schedule received. This analysis will not be stratified. Due to the random treatment assignment with stratification for the timing of reconstruction and type of reconstruction, it is expected that the baseline patient characteristics, including the planned reconstruction procedures, are roughly balanced across the two treatment arms. A sensitivity analysis stratified by timing and type of reconstruction surgery will be conducted.

The frequency and the proportion of patients who enrolled in the trial prior to reconstruction surgery who did not receive the surgery within 18 months of radiation as specified in the eligibility criteria will be summarized separately by arm. A secondary analysis excluding these patients will be conducted.

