12.4.2 Photographic Cosmetic Assessment

Reconstructed breast photographic cosmetic scores 24 months after radiation with hypofractionated radiation compared to standard fractionation: Two year photographic cosmetic scores will be summarized by treatment arm and will be compared across the treatment arms using a Wilcoxon rank-sum test with a two-sided alternative. The proportions of patients with poor global cosmetic score (defined as a cosmetic score of 3: poor or large difference) at 24 months after radiation will be summarized separately by treatment arm and will be compared using a two-sample test of proportions with a two-sided alternative.

Reconstructed breast photographic cosmetic scores 24 months after radiation based on the method and timing of reconstruction received: Two year photographic cosmetic scores and the proportions of patients with poor global cosmetic score will be assessed separately by timing and method of reconstruction subgroups using similar method described above.

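### The overall cosmetic comparison ignores the factors that balance the allocation; if they affect cosmesis, the test is valid but conservative, and stratifying it is a free improvement

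*Combined protocol and SAP*

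**What the plan says.** - **Allocation (section 4.6).** "Patients will be stratified before randomization based on planned intent for" autologous (with or without implant) versus implant only, and also by immediate versus planned delayed reconstruction. The method is Pocock-Simon, which "balances the marginal distributions of the stratification factors between the treatment groups".
- **Overall cosmetic test (section 12.4.2).** The two-year scores "will be compared across the treatment arms using a Wilcoxon rank-sum test with a two-sided alternative". The proportion with a poor global score, defined as 3, is compared by a two-sample test of proportions. Neither test names strata.
- **Cosmesis by subgroup (section 12.4.2).** Scores and poor-score proportions "will be assessed separately by timing and method of reconstruction subgroups using similar method described above". The matching objective in section 2.3 is "To evaluate reconstructed breast photographic cosmetic scores 24 months after radiation based on the method and timing of reconstruction received".
- **Primary endpoint (section 12.3.2).** The main analysis is explicitly unstratified. Baseline balance is expected because of the "stratification for the timing of reconstruction and type of reconstruction", and the plan then adds: "A sensitivity analysis stratified by timing and type of reconstruction surgery will be conducted". No such statement is made for cosmesis.
- **Scale (section 1.5).** "Characteristics are graded on a four-point scale: 0, excellent or no difference; 1, good or small difference", with 2 for a moderate and 3 for a large difference.

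**The concern.** When allocation is balanced on a prognostic factor, differences between its levels largely cancel from the arm contrast. A test that ignores the factor still counts those differences as noise. Its standard error is then too large, its actual type I error falls below nominal, and it detects a true difference less often than a test that uses the strata.

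This bears on a question the sponsor cares about. Better cosmesis with hypofractionation is one of the hypotheses in section 1.6, and section 10.6 treats the cosmetic result as an important outcome. Because the hypothesis is one of benefit, a conservative test works against it. The number scored may also fall below the 792 evaluable patients, since section 10.6 leaves out patients with ipsilateral or nodal recurrence before the 24-month photograph.

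**Working it through.** **1. The plan's own figure.** Cosmesis has no stated sample size, effect, alpha or power. The only stated design figure is for the primary endpoint (section 12.2), and it reproduces: n per arm = (1.960 + 1.282)² × 2 × 0.25 × 0.75 / 0.10² ≈ 394, or 395 from the routine used, against 396 stated; 792 / 0.9 = 880. So 792 is used as the number scored.

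**2. Why the test is conservative.** Let R² be the share of score variance explained by the strata. With balanced allocation the variance of the arm contrast shrinks by about (1 − R²), while the unstratified test uses the full variance. Hence

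actual alpha ≈ 2 × {1 − Φ(1.96 / √(1 − R²))}.

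- R² = 0.10: 1.96 / 0.949 = 2.066, alpha 3.9%.
- R² = 0.20: 1.96 / 0.894 = 2.191, alpha 2.8%.
- R² = 0.30: 1.96 / 0.837 = 2.343, alpha 1.9%.

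**3. Simulation under minimisation.** From the documents: 792 patients, two binary balancing factors, Pocock-Simon allocation, a four-category score. Assumed, because the documents do not give them: factor prevalences 50% and 35%, biased-coin probability 0.8, overall score split 20/30/30/20%, arm effect 0.2 latent SD, two-sided alpha 0.05, and R² itself.

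The unstratified test is the tie-corrected Wilcoxon. The van Elteren statistic is Z = Σ w_g U_g / √(Σ w_g² V_g), with w_g = 1/(N_g + 1), U_g the centred rank sum in stratum g and V_g its tie-corrected variance, over the four type-by-timing cells. There were 8,000 null and 4,000 alternative trials per setting.

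| R² | Type I error: Wilcoxon | Type I error: van Elteren | Power: Wilcoxon | Power: van Elteren | Power lost |
|---|---|---|---|---|---|
| about 0 | 5.0% | 5.0% | 74.1% | 74.1% | 0 |
| 4% | 4.8% | 5.1% | 72.6% | 73.8% | 1 |
| 10% | 3.8% | 5.0% | 69.6% | 73.4% | 4 |
| 17% | 3.5% | 5.2% | 66.3% | 72.4% | 6 |
| 30% | 2.2% | 5.6% | 59.1% | 72.2% | 13 |

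The standard error of a null rate is √(0.05 × 0.95 / 8,000) = 0.24 points. The 5.6% is therefore about 2.5 standard errors above nominal. A longer run of that setting did not repeat the excess, so it is read as simulation noise.

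**4. Source of the conservatism.** With simple randomisation and R² of 30%, the Wilcoxon type I error is 5.0%. The shortfall therefore comes from the balanced allocation.

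**5. A second set of assumptions.** With 340 per arm, balance within four strata (shares 15/25/25/35%), treatment odds ratio 1.5 and equal log-odds steps between strata, the odds ratio between extreme strata is exp(3 × step).

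| Step | Extreme-strata odds ratio | Power: Wilcoxon v van Elteren |
|---|---|---|
| 0.2 | 1.8 | 83.5% v 84.1% |
| 0.3 | 2.5 | 82.3% v 83.5% |
| 0.4 | 3.3 | 81.1% v 82.8% |
| 0.5 | 4.5 | 80.3% v 83.0% |
| 0.8 | 11 | 78% v 84% |
| 1.2 | 37 | 67% v 83% |

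For the score-of-3 proportion, a Cochran-Mantel-Haenszel test gained 0.5 to 2 points at steps 0.3 to 0.5, and 4 points at 0.8.

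**6. What the documents say about R².** They give no cosmetic score by type or timing. Section 1.2 gives complications: 44% immediate against 22% delayed in one cited series, 52% against 33% in another, and none with autologous tissue in a third whose severe complication rate was 25%. Section 9.2.3 grades capsular contracture partly by appearance. That makes some prognostic effect on cosmesis plausible but does not measure it.

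**The case against.** A reader might infer that reconstruction type and timing are known to drive cosmesis, so that the cosmetic p-value is certainly too large. The documents do not support that. Whether cosmesis varies by method and timing is itself an objective (section 2.3), and section 1.2 reports complications. The score is also graded against the other side of the chest, so complication differences need not carry over.

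A reader might also take the 13-point loss, or the 16 points at the steepest step above, as the expected size. Those are the upper part of an assumed range. A 2.5- to 4.5-fold odds difference between extreme strata costs only about 1 to 3 points.

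Three further points favour the plan:

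- The unstratified approach is deliberate for the primary endpoint, and the other secondary between-arm tests are mostly simple two-sample tests too. This stands as a reason to keep the unstratified tests as supportive, but the primary endpoint also gets a stratified sensitivity analysis, which cosmesis lacks.
- Section 12.4.2 does look at cosmesis by timing and method. True, but separate subgroup comparisons recover no power for the overall question. They also use the reconstruction received, which for delayed patients is settled after randomisation.
- This is a secondary endpoint with no stated power, and the Wilcoxon test is valid. Both are correct, and they limit the point to an improvement in efficiency.

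**Conclusion.** The point holds conditionally. The overall cosmetic tests are unstratified although allocation is balanced on planned type and timing. If those factors are prognostic for cosmesis, the tests are conservative and lose power relative to stratified versions: about 0 points at R² of 0%, 1 at 4%, 4 at 10%, 6 at 17% and 13 at 30%, with type I error falling from 5.0% to about 2.2%. These sizes rest on the assumptions in the working, above all on R², which the documents do not supply.

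It would be wrong to conclude that the cosmetic analysis is invalid or that it misses a design target. Type I error is not inflated, and no cosmetic power is stated. The case for change is that stratifying cost nothing when the strata carried no information (74.1% against 74.1% power, 5.0% against 5.0% type I error) and gained power when they did.

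**What to change.** In section 12.4.2:

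- Compare the score between arms with a van Elteren test, or a proportional-odds model that includes the two factors.
- Compare the proportion with a score of 3 by a Cochran-Mantel-Haenszel test on the same strata, leaving the cut-point as it is.
- Define the strata as planned type and planned timing as recorded at randomisation, not the reconstruction received.
- Keep the unstratified tests as supportive, for consistency with the primary analysis.

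At minimum, extend the stratified sensitivity analysis of section 12.3.2 to the two cosmetic comparisons.

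The cost is SAP wording, to be fixed before cosmetic data are compared by arm. No new data, visits or patients are needed.

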12.4.3 Lymphedema Assessment

Incidence of arm lymphedema by treatment arm: The proportions of patients with arm lymphedema (defined as a change of 10% or greater in ipsilateral arm volume from the pre-RT volume, see also Section 10.3.1 for definition of arm lymphedema) at 2 year post radiation will be summarized and will be compared across the two treatment arms using a two-sample test of proportions (Z test) with a two-sided alternative. Change in ipsilateral arm volume at each of the following time-points: 6, 12, 24 and 60 months post-radiation (relative to pre-RT) will be compared using a two sample t-test with a two-sided alternative. The changes in arm volume at these time points will also be analyzed as a repeated measure using a linear mixed model with patient as the random effect.

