2.4 Lymphedema Assessment

- 2.4.1** To estimate the incidence of arm lymphedema by treatment arm.

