10.5.1 Clinical Assessment

All planned lymphedema evaluations will include clinical assessment for signs and symptoms of lymphedema. Any patient complaining of “arm swelling” or “heaviness” or showing signs of extremity swelling (≥ 2 cm difference between upper extremities at any measurement point) will be treated according to current practice guidelines and referred to a lymphedema health care provider. In addition, patients will be instructed to call their oncologist if they develop any new arm symptoms during the periods between planned assessments. Such patients will be scheduled for immediate evaluation and arm measurements.

Arm Measurement: Circumferential measurement of limb volume will be performed on both affected and non-affected arms. Patients will sit with the arms resting horizontally palms-down on a bedside table placed at a level slightly below the axilla. The patients will be instructed to wear loose sleeves or short sleeves/sleeveless tops and to remove any arm jewelry prior to the measurement. Measurements will be taken at the wrist, half way between the wrist and antecubital fossa (below the elbow), at the antecubital fossa, half way between the antecubital fossa and the axilla, and at the axilla. In all cases, the plane of the tape around the arm will be held perpendicular to the long axis of the arm and perpendicular to the floor. The tape will be held snugly around the body part without indenting the skin or compressing subcutaneous adipose tissue. If gaps between the skin and tape are seen in some individuals, tension should not be increased to reduce the gap. Arm measurements and other required data will be recorded on the Arm circumference measurement case report form (Appendix IV) which is to be completed by the local study coordinator. The standard formula (based on cylindrical slices) will be utilized in this study to calculate volume (V) from circumference (U) measures.

PowerPoint slides located on the A221505 study page will provide instructions on how to perform these measurements. The procedures used in CALGB 70305 will be followed in this study.

Arm Lymphedema: A patient will be considered to have mild lymphedema if she has symptomatic arm swelling or heaviness with less than a 10% increase in volume of the ipsilateral arm from pre-radiation volume.

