APPENDIX IV: ARM CIRCUMFERENCE MEASUREMENTS*(Page 1 of 2)*Reporting Period: *(check one)*☐ Prior to radiation☐ 6 month follow-up visit☐ 24 month follow-up visitHave the lymphedema measurements been performed? *(check one)* ☐ Yes ☐ NoIf No, reason not performed: *(check one)*☐ Patient refusal☐ Site staff forgot to perform☐ Other, specify _____

If Yes, complete the rest of this form including the body diagram

Date: *(dd MMM yyyy)* ____ - ____ - ____Side breast cancer surgery performed: *(check one)* ☐ Right ☐ Left

Height ____ . ____ cm

Weight: ____ . ____ kg

BMI ____ . ____ *(derived field)*Has the patient reported difficulties with arm lymphedema since the last visit? *(check one)* ☐ Yes ☐ No

If Yes, treatment/interventions for arm lymphedema:

Exercises ☐ Yes ☐ NoCompression garment ☐ Yes ☐ NoLymphatic massage ☐ Yes ☐ NoBenzopyrones ☐ Yes ☐ NoSkin care ☐ Yes ☐ No☐ Other, specify _____

Body Diagram

(Page 2 of 2)

INSTRUCTIONS:

1. **Mark an X on the diagram where the breast cancer surgery occurred.**
2. Using a tape measure, obtain arm circumference measurements at the locations indicated below. Measurements should be rounded to the nearest 0.10 cm.
 - a. Determine the halfway point distance above and below the antecubital fossa at the baseline visit. Record the distance for reference at future visits. Record the halfway point from antecubital fossa to axilla as the distance above the antecubital fossa. Record the halfway point from antecubital fossa to wrist as the distance below the antecubital fossa. *** Use halfway point measurements documented at Baseline. Do not repeat halfway point measurement at each visit.**
3. Circumferential arm measurements will be completed by the study staff. Open Rave and complete the Arm Circumference Measurements Form.

RIGHT**Halfway point ***

Distance above antecubital fossa: ____ . ____ cm

Distance below antecubital fossa: ____ . ____ cm

Circumference

[figure not shown]
Axilla: ____ . ____ cm

Halfway from antecubital fossa to axilla: ____ . ____ cm

Antecubital fossa (just above elbow joint): ____ . ____ cm

Halfway from antecubital fossa to wrist: ____ . ____ cm

Wrist: ____ . ____ cm

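### The arm lymphedema objective is incidence, but 12.4.3 tests status at the 2-year visit only, so a 6-month case that is below 10% at 24 months counts as a non-case

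*Combined protocol and SAP*

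**What the plan says.** Section 2.4.1 states the objective: "To estimate the incidence of arm lymphedema by treatment arm". Section 12.4.3 repeats the incidence label and sets the case criterion, "defined as a change of 10% or greater in ipsilateral arm volume from the pre-RT volume". It then fixes the time at two years: "for definition of arm lymphedema) at 2 year post radiation will be summarized and will be compared across the two treatment arms". The test is a "two-sample test of proportions (Z test) with a two-sided alternative". No rule says that a patient counts if the criterion was met at any point up to two years.

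Arm circumferences are scheduled before radiation, at 6 months and at 2 years (Sections 5.0 and 10.5). Under 10.5.1, a patient who complains of arm swelling or heaviness, or whose arms differ by 2 cm or more at any measuring point, "will be treated according to current practice guidelines and referred to a lymphedema health care provider". For new arm symptoms between planned assessments, 10.5.1 adds: "Such patients will be scheduled for immediate evaluation and arm measurements". Section 10.5 stops the arm assessments in patients with a new or recurrent breast cancer.

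The Appendix IV form offers three reporting periods: before radiation, 6 months and 24 months. Under the line "If Yes, treatment/interventions for arm lymphedema" it has yes/no boxes, including exercises and skin care, with no start dates.

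**The concern.** Incidence asks how many patients developed lymphedema over the period. Status at 24 months asks how many have it on that day. The two agree only if no case falls back below the threshold, and this protocol requires early swelling to be treated. The statistic can therefore understate the quantity that the objective names.

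Section 1.6 hypothesises reduced lymphedema with hypofractionation, so the comparison will be read as evidence on that hypothesis. At stake are the absolute incidence reported for each arm, the absolute difference between arms, and the precision of a secondary comparison. The primary endpoint is not affected.

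**Working it through.** **1. Who is counted.** Apply 12.4.3 as written to the scheduled measurements:

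| 6 months | 24 months | Counted in 12.4.3 | Incident case by the 10% criterion |
|---|---|---|---|
| 10% or more | 10% or more | yes | yes |
| below 10% | 10% or more | yes | yes |
| 10% or more | below 10% | no | yes |
| 10% or more | missing (e.g. assessments stopped) | no rule | yes |
| below 10% | below 10% | no | not by scheduled visits |

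The third and fourth rows are the gap.

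**2. Whether another analysis fills it.**
- The t-tests and mixed model in 12.4.3 compare mean volume change, not the proportion affected.
- CTCAE lymphedema is graded at visits to 5 years (5.0), but 12.4.1 analyses acute or late complications together, and 10.2 defines late ones as grade 3 or higher.
- The LBCQ asks about past symptoms, and 12.4.4 analyses it as a score.

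None yields incidence by the 10% criterion.

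**3. The plan's own figures.** Section 12.2 gives 396 evaluable patients per arm for the primary endpoint. With a 25% rate in both arms, a 10-point margin, one-sided 0.025 and 90% power:

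n = (1.960 + 1.282)² × 2 × 0.25 × 0.75 / 0.10² ≈ 394, which the calculation run without rounding puts at 395 per arm.

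This agrees with 396, where power is 90.1%. At a 50% control rate it is 80.4%, against a stated figure of about 80%. Also 792 / 0.90 = 880. No sample size or power is stated for lymphedema, so no lymphedema figure can be shown wrong. I use 396 per arm as the largest denominator.

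**4. Illustration of size (assumed inputs).** Let C be cumulative incidence by the 10% criterion and f the share of cases below 10% at 24 months. Then

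24-month proportion = C × (1 − f).

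The documents give no f. I assume 25% and 50%, with C = 20% against 14%. The 20% is the low end of the 20–40% that 1.4.1 reports after axillary dissection, where case definitions vary. The 14% is an assumption. Power = Φ(|difference| / SE − 1.96), with SE = √[(p₁(1−p₁) + p₂(1−p₂)) / 396] and two-sided 0.05 assumed:

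| f in both arms | Proportions seen | Difference | Risk ratio | Power |
|---|---|---|---|---|
| 0 | 20% v 14% | 6.0 points | 0.70 | 62% |
| 25% | 15% v 10.5% | 4.5 points | 0.70 | 48% |
| 50% | 10% v 7% | 3.0 points | 0.70 | 33% |

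At C = 20% there are 396 × 0.20 = 79.2 cases in an arm, of which 19.8 (f = 25%) or 39.6 (f = 50%) are not counted. At C = 7%, the grade 2 or higher figure that 1.2 cites from a regional nodal irradiation trial, the 24-month proportion would be 5.25% or 3.5%.

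**5. Unequal resolution.** If C = 30% with f = 50% in one arm and C = 20% with f = 25% in the other, both show 15% (0.30 × 0.50 = 0.20 × 0.75). This is an arithmetic possibility only.

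**The case against.** The strongest reply is that status at a fixed time, whatever the treatment, is a legitimate and common endpoint, so the fault is mainly in the label. That stands as a reason to keep the 24-month proportion. It does not supply the incidence that 2.4.1 asks for.

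A second reply is that the phrase may be loose. Objective 2.1 speaks of a rate at 24 months, which 12.3.2 makes explicit as within two years. But 12.4.3 has no such clarification, while 12.4.1 does specify cumulative incidence for recurrence. A status at the visit is the likelier reading.

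Third, earlier swelling does not go unseen. The 6-month mean change, the mixed model and CTCAE grading would all register it. This is right and limits the consequence.

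A reader might infer that everyone treated early is scored as never having had lymphedema. The documents do not support that. Treated patients still at 10% or more are counted. The referral trigger (symptoms or 2 cm between arms) is not the 10% criterion, so some referred patients were never cases; 10.5.1 itself classes symptomatic patients with an increase below 10% as mild.

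A reader might also infer that the snapshot can hide or reverse an arm difference. That needs resolution to differ by arm. The trial is unblinded, but nothing in the documents shows such a difference.

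**Conclusion.** The mismatch holds: the objective is incidence, the planned statistic is 24-month prevalence, and no other planned analysis supplies incidence by the same criterion. The patients affected are those at 10% or more at 6 months who are below 10%, or have no value, at 24 months.

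The size is unknown. Under assumed resolution of 25% to 50%, the 24-month proportion falls short of cumulative incidence by the same 25% to 50%. With equal resolution the risk ratio is preserved while the absolute difference and power fall. The power figures rest on assumed rates, on 396 measured patients per arm and on an assumed two-sided 0.05. They illustrate the direction and do not estimate a loss. The matter concerns a secondary objective and is worth settling before analysis.

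**What to change.** In 12.4.3, define incidence as an increase of 10% or more from pre-radiation ipsilateral volume at either scheduled post-radiation measurement (6 or 24 months). A 6-month case then counts even if the 24-month value is below 10% or missing. State the denominator as well: how a 6-month non-case without a 24-month value is handled, since dropping only such patients would push the proportion up. Report the 24-month proportion separately as prevalence.

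Do not make the Appendix IV treatment boxes a case criterion. They carry no start dates, include exercises and skin care, and would turn patients below 10% into cases. Report treatment descriptively. Add unscheduled measurements only as a sensitivity analysis, and only if they are confirmed to be recorded, because the form has no reporting period for them.

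The same edit can settle three smaller points in 12.4.3. Its criterion gives no direction of change. Its cross-reference to 10.3.1 leads to local recurrence rather than to 10.5.1. It lists 12- and 60-month volumes that 5.0, 10.5 and Appendix IV do not schedule.

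The cost is wording and programming on scheduled data. The downside is that an ever-met definition also counts transient or measurement-error crossings of 10%, which the retained prevalence puts in context. It still misses cases that arise and resolve between the two visits.
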